9.1.3 Serious Adverse Events

A serious adverse event is defined as an adverse event that meets at least 1 of the following serious criteria (unless it meets the definition of a Disease-Related Event as defined in [Section 9.1.1](#)):

- fatal
- life threatening (places the subject at immediate risk of death)
- requires in patient hospitalization or prolongation of existing hospitalization
- results in persistent or significant disability/incapacity
- congenital anomaly/birth defect
- other medically important serious event

A Disease-Related event is to be reported as a serious adverse event if the event meets at least 1 of the serious criteria above.

An adverse event would meet the criterion of “requires hospitalization”, if the event necessitated an admission to a health care facility (eg, overnight stay).

If an investigator considers an event to be clinically important, but it does not meet any of the serious criteria, the event could be classified as a serious adverse event under the criterion of “other medically important serious event”. Examples of such events could include allergic bronchospasm, convulsions, blood dyscrasias, drug induced liver injury (DILI) (see [Appendix A](#) for DILI reporting criteria), or events that necessitate an emergency room visit, outpatient surgery, or urgent intervention.

9.2 Safety Event Reporting Procedures

9.2.1 Reporting Procedures for Disease-Related Events

The investigator is responsible for ensuring that all Disease-Related Events observed by the investigator or reported by the subject that occur after the first dose of investigational medicinal product(s)/ study treatment/ protocol-required therapies through the End of Study are recorded on the Event eCRF as a Disease-Related Event.

All serious disease-related events will be recorded and reported to the sponsor or designee within 24 hours. The investigator will submit any updated serious disease-related event data to the sponsor within 24 hours of it being available.

Disease-related events assessed by the investigator to be more severe than expected and/or related to the investigational product(s)/study treatment/protocol-required therapies, and determined to be serious, must be reported on the Event CRF as serious adverse events and recorded and reported per [section 9.2.1](#) and [Appendix I](#).

Disease-related events pre-defined for this study are listed in [Table 18](#).

Additionally, the investigator is required to report a fatal Disease-Related Event on the Event eCRF as a Disease-Related Event.

9.2.2 Adverse Events

9.2.2.1 Reporting Procedures for Adverse Events That do not Meet Serious Criteria

The investigator is responsible for ensuring that all adverse events observed by the investigator or reported by the subject that occur after the first dose of investigational product through the End of Study are reported using the Event eCRF.

The investigator must assign the following adverse event attributes:

- Adverse event diagnosis or syndrome(s), if known (if not known, signs or symptoms),
- Dates of onset and resolution (if resolved),
- Severity,
- Assessment of relatedness to investigational product, medical devices or other protocol-required therapy, and
- Action taken.

The adverse event grading scale used will be the CTCAE, version 4.0. The grading scale used in this study is described in [Appendix A](#). The investigator must assess whether the adverse event is possibly related to the investigational product, medical device(s), and/or other protocol-required therapies. This relationship is indicated by a “yes” or “no” response to the question: Is there a reasonable possibility that the event may have been caused by the investigational product?

The investigator must assess whether the adverse event is possibly related to any study mandated activity (eg, administration of investigational product, protocol-required therapies, use of medical device(s) and/ or procedure (including any screening procedure(s))). This relationship is indicated by a “yes” or “no” response to the question: “Is there a reasonable possibility that the event may have been caused by administration of investigational product?”

The investigator is responsible for reviewing laboratory test results and determining whether an abnormal value in an individual study subject represents a clinically significant change from the subject’s baseline values. In general, abnormal laboratory findings without clinical significance (based on the Investigator's judgment) are not to be recorded as adverse events. However, laboratory value changes that require treatment

or adjustment in current therapy are considered adverse events. Where applicable, clinical sequelae (not the laboratory abnormality) are to be recorded as the adverse event.

The investigator is expected to follow reported adverse events until stabilization or reversibility.

9.2.2.2 Reporting Procedures for Serious Adverse Events

The investigator is responsible for ensuring that all serious adverse events observed by the investigator or reported by the subject that occur after signing of the informed consent through 30 days after the last day of the dosing interval of the investigational product or the end of study visit (whichever is later) are recorded in the subject's medical record and are submitted to Amgen. All serious adverse events must be submitted to Amgen within 24 hours following the investigator's knowledge of the event via the Event eCRF.

If the electronic data capture (EDC) system is unavailable to the site staff to report the serious adverse event, the information is to be reported to Amgen via an electronic Serious Adverse Event (eSAE) Contingency Report Form within 24 hours of the investigator's knowledge of the event. See [Appendix B](#) for a sample of the Serious Adverse Event Worksheet/electronic Serious Adverse Event Contingency Report Form. For EDC studies where the first notification of a Serious Adverse Event is reported to Amgen via the eSerious Adverse Event Contingency Report Form, the data must be entered into the EDC system when the system is again available.

The investigator must assess whether the serious adverse event is possibly related to the investigational product, medical device(s), and/or protocol-required therapies. This relationship is indicated by a "yes" or "no" response to the question: Is there a reasonable possibility that the event may have been caused by the investigational product. Relatedness means that there are facts or reasons to support a relationship between investigational product and the event.

The investigator is expected to follow reported serious adverse events until stabilization or reversibility.

New information relating to a previously reported serious adverse event must be submitted to Amgen. All new information for serious adverse events must be sent to Amgen within 24 hours following knowledge of the new information. If specifically requested, the investigator may need to provide additional follow-up information, such as

discharge summaries, medical records, or extracts from the medical records. Information provided about the serious adverse event must be consistent with that recorded on the Event eCRF.

If a subject is permanently withdrawn from protocol-required therapies because of a serious adverse event, this information must be submitted to Amgen.

Amgen will report serious adverse events and/or suspected unexpected serious adverse reactions as required to regulatory authorities, investigators/institutions, and IRBs/IECs in compliance with all reporting requirements according to local regulations and good clinical practice.

The investigator is to notify the appropriate IRB/IEC of serious adverse events occurring at the site and other adverse event reports received from Amgen, in accordance with local regulatory requirements and procedures.

9.2.2.3 Reporting Serious Adverse Events After the Protocol-required Reporting Period

There is no requirement to monitor study subjects for serious adverse events following the protocol-required reporting period or after end of study. However, these serious adverse events can be reported to Amgen. In some countries (eg, European Union [EU] member states), investigators are required to report serious adverse events that they become aware of after end of study and that are considered related to the investigational product by the investigator. If serious adverse events are reported, the investigator is to report them to Amgen within 24 hours following the investigator's knowledge of the event.

In addition to the attributes listed in [Section 9.2.2.1](#), the investigator must also complete the serious adverse event section of the Event eCRF.

Serious adverse events reported outside of the protocol-required reporting period will be captured within the safety database as clinical trial cases for the purposes of expedited reporting.

9.3 Pregnancy and Lactation Reporting

If a female subject becomes pregnant, or a male subject fathers a child, while the subject is taking protocol-required therapies report the pregnancy to Amgen Global Patient Safety as specified below.

In addition to reporting any pregnancies occurring during the study, investigators should report pregnancies that occur through 30 days after the last dose of AMG 596 or through 4 months (120 days) after the last dose of AMG 404.

The pregnancy should be reported to Amgen Global Patient Safety within 24 hours of the investigator's knowledge of the pregnancy. Report a pregnancy on the Pregnancy Notification Worksheet (see [Appendix C](#)). Amgen Global Patient Safety will follow-up with the investigator regarding additional information that may be requested.

If a female subject becomes pregnant during the study, the investigator should attempt to obtain information regarding the birth outcome and health of the infant.

If the outcome of the pregnancy meets a criterion for immediate classification as a Serious Adverse Event (eg, female subject experiences a spontaneous abortion, stillbirth, or neonatal death or there is a fetal or neonatal congenital anomaly) the investigator will report the event as a Serious Adverse Event.

If a female breastfeeds while taking protocol-required therapies report the lactation case to Amgen as specified below.

In addition to reporting a lactation case during the study, investigators should report lactation cases that occur through 30 days after the last dose of protocol-required therapies.

Any lactation case should be reported to Amgen Global Patient Safety within 24 hours of the Investigator's knowledge of event. Report a lactation case on the Lactation Notification Worksheet ([Appendix C](#)) Amgen Global Patient Safety will follow-up with the investigator regarding additional information that may be requested.

If a male subject's female partner becomes pregnant, the investigator should discuss obtaining information regarding the birth outcome and health of the infant from the pregnant partner.

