3.4.1 Study Duration for Subjects

It is anticipated that an individual subject will participate in the study for approximately 8 months including an effective screening period lasting 14 days, a treatment period lasting approximately 4 to 6 months, and a safety follow up period lasting 30 days (+/- 7 days). Additionally, there is a long term follow up for up to 12 months from treatment initiation. The actual duration for individual subjects will vary depending upon tolerability of AMG 596, evidence of clinical progression, and willingness to participate in the study.

In the event that a subject demonstrates clinical benefit from therapy, he or she may continue treatment with AMG 596 until he or she experiences an unacceptable adverse event, clinically significant disease progression, or he or she wishes to withdraw consent.

The safety follow-up study visit (SFUP) should occur 30 days (+/- 7 days) after the last dose of AMG 596 or prior to the initiation of other therapy, whichever occurs first. End of study for an individual subject is defined as the date of the final long-term follow up study visit (LTFU) when assessments and procedures are performed.

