3.4.2 End of Study

Primary Completion: the time when the last subject is assessed or receives an intervention for the purposes of final collection of data for the primary analysis; a primary analysis will be performed for each group separately when target enrollment in Part 1 and Part 2 is complete and each subject either completes 6 months on study or withdraws from the study.

End of Study: the time when the last subject is assessed or receives an intervention for evaluation in the study. The final analysis will occur at this time.

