210. Treatment with non-topical systemic corticosteroids within 14 days before enrollment (day 1) (exemption: prophylactic treatment with dexamethasone as defined in [section 6.5](#), and systemic corticosteroid doses of ≤ 2 mg of dexamethasone (or equivalent) per day after consultation with Sponsor,)
211. Prior participation in an investigational study (drug, procedure or device) within 21 days of study day 1
212. Major surgery within 7 days of study day 1 with the exception of biopsy and long line insertion
213. History or evidence of any other clinically significant disorder, condition or disease that, in the opinion of the investigator or Amgen physician, if consulted, would pose a risk to subject safety or interfere with the study evaluation, procedures or completion
214. Male and female of reproductive potential who are unwilling to practice highly effective method(s) of birth control while on study and through 30 days after receiving the last dose of AMG 596 and through 4 months (120 days) after receiving the last dose of AMG 404.
 - Criteria for women of non-reproductive potential is as follows:
 - Postmenopausal as defined as:
 - Age of 55 years with cessation of menses for 12 months or more, OR
 - Age < 55 years and no spontaneous menses for at least 2 years, OR
 - Age < 55 years and spontaneous menses within the past year, but currently amenorrheic (eg, spontaneous or secondary to chemotherapy) AND with postmenopausal gonadotropin levels (luteinizing hormone and follicle-stimulating hormone level > 40 IU/L) or postmenopausal estradiol levels (< 5 ng/dL) according to the definition of “postmenopausal range” for the laboratory involved; OR
 - History of hysterectomy; OR
 - History of bilateral oophorectomy

Highly effective methods of birth control include sexual abstinence (male, female); vasectomy; bilateral tubal ligation/occlusion; hormonal birth control or intrauterine device (IUD) (female).

215. Female who is lactating/breastfeeding or who plans to breastfeed while on study through 30 days after receiving the last dose of AMG 596 and through 4 months (120 days) after receiving the last dose of AMG 404.
216. Female with a positive pregnancy test.
217. Female planning to become pregnant while on study through 30 days after receiving the last dose of AMG 596 and through 4 months (120 days) after receiving the last dose of AMG 404 infusion.

Approved

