7.2.5 Long Term Follow Up

The long term follow up visit (LTFU) is to be performed via clinical visit or telephone every 3 months (+/- 2 weeks) after their SFUP visit and until a maximum of 12 months from start of treatment, until start of a new therapy or until death has been reported, whichever occurs first.

Subjects will allow Amgen continued access to medical records for up to 12 months from start of treatment, so that information related to subject's disease status may be obtained. All efforts should be made to conduct this visit. If it is not possible to conduct the LTFU visit, documentation of the efforts to complete the visit should be provided in the source documents and noted as not done in the eCRF.

The following procedures will be completed at the LTFU visit as designated in the Schedules of Assessments ([Section 7.1](#)):

- Method of contact (clinical study visits or telephone contact)
- Adverse Events and Serious Adverse Events with respective Concomitant Medications
- Imaging assessments (if collected as part of SoC) and treatment response (if available)

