8.3.2 Reasons for Removal From Study

Reasons for removal of a subject from the study are:

- decision by sponsor (eg, product quality issue)
- withdrawal of consent from study
- death
- lost to follow-up
- start of any other antitumor therapy

Approved

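### Protocol 9.3 stops post-treatment lactation reporting at 30 days, although pregnancy reporting and the breastfeeding restriction run to 120 days after AMG 404 (minor, Arm 2 only)

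*Protocol*

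**What the plan says.** Protocol Section 9.3 handles pregnancy and lactation in parallel paragraphs. Each asks for cases during the study and then adds a post-treatment window.

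- Pregnancy: "through 30 days after the last dose of AMG 596 or through 4 months (120 days) after the last dose of AMG 404".
- Lactation: "investigators should report lactation cases that occur through 30 days after the last dose of protocol-required therapies". There is no separate limit for AMG 404.

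The next lactation paragraph gives the investigator 24 hours from learning of a case to report it. That sentence has no day limit.

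Exclusion 215 in Section 4.2 rules out women who breastfeed or plan to do so on study, for 30 days after AMG 596 and "through 4 months (120 days) after receiving the last dose of AMG 404".

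The end of the study is defined twice. Section 3.4.1 ends it for a subject at her final long-term follow-up visit. Section 3.4.2 ends it for the trial at "the time when the last subject is assessed or receives an intervention for evaluation in the study". Section 9.3 does not say which applies to lactation reporting.

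**The concern.** The protocol treats days 31 to 120 after AMG 404 as a period in which breastfeeding should not happen. It wants pregnancies in that period reported, yet its post-treatment lactation window has already closed. Neither document explains the difference.

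It looks like an omission. The Amendment 5 change log, used here only as history, shows that the pregnancy sentence had a 30-day limit tied to protocol-required therapies until AMG 404 was added. The same amendment lengthened exclusion 215. The lactation sentence still has the older form.

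At stake is a notification rule for a rare infant exposure, in a combination for which Section 2.5.3.2 says there is no clinical safety information. The statistical analysis is not at stake.

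**Working it through.** The plan states no figure to reproduce. The check is a comparison of windows and one subtraction.

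**Windows after the last dose**

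| Rule | After AMG 596 | After AMG 404 |
|---|---|---|
| Pregnancy reporting (9.3) | 30 days | 120 days |
| Breastfeeding restriction (exclusion 215) | 30 days | 120 days |
| Lactation reporting (9.3) | 30 days after the last protocol-required therapy | same clause, no separate limit |

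**Arm 1.** All three rules give 30 days, so there is no mismatch.

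**Arm 2.** Count from the last AMG 404 dose. If AMG 404 is the last product given and the woman has left the study by day 30:

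shortfall = 120 - 30 = 90 days (day 31 to day 120).

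This is a maximum. If AMG 596 continues after the last AMG 404 dose, the 30 days start later and the shortfall is smaller.

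**Does the in-study duty fill the gap?** That depends on which end of study is meant.

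- *Trial-wide (3.4.2).* While the trial is open, every case falls during the study and the shortfall is 0.
- *Subject level (3.4.1).* Cover lasts only as long as she remains in the study, and 120 days is not guaranteed. Under 7.2.5, long-term follow-up takes place "every 3 months (+/- 2 weeks) after their SFUP visit and until a maximum of 12 months from start of treatment" and ends sooner with a new therapy or death. Section 8.3.2 removes a subject from the study on "start of any other antitumor therapy", on withdrawal of consent, on loss to follow-up or by sponsor decision. A woman who stays in follow-up for 120 days after AMG 404 has no gap.

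**Do the serious adverse event rules fill it?** No. Section 9.2.2.3 states: "There is no requirement to monitor study subjects for serious adverse events following the protocol-required reporting period or after end of study". Those rules also concern serious events, and a lactation exposure need not be one.

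**Does the 24-hour sentence fill it?** Possibly. It can be read as a deadline for cases already inside the windows above it, or as a duty to report any case that becomes known. The text does not settle this.

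**How many women?** The documents give no count. Exclusions 215 to 217 keep out women who are lactating, pregnant, or planning either, and pregnancy ends treatment under Section 6.2.5. A case would need a woman to begin breastfeeding after treatment despite these restrictions, and to have left the study.

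**The case against.** The strongest reply is that the gap may not exist. Section 9.3 asks first for cases during the study, and the 30-day clause only adds to that. On the trial-wide reading nothing is lost while the trial is open. The 24-hour sentence could also cover every case that becomes known. Both readings are available, so a reader who infers that an exposure would certainly go unreported goes further than the text allows. Equally, neither reading is stated, so the 30-day limit remains the only explicit post-treatment rule.

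A second reply is that a reporting window need not equal an avoidance window, and that the right lactation window depends on AMG 404 data that these documents do not contain. That is fair, and no claim is made here that 120 days is pharmacologically required. What stands is the inconsistency: for pregnancy, the protocol reports for as long as it restricts; for lactation it does not, and it gives no reason.

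A third reply is that the affected group is nearly empty. That is accepted, and it is why the point is minor.

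A reader might also infer from Section 7.3.13, which names only AMG 596 when ordering discontinuation after a confirmed positive pregnancy test, that AMG 404 could continue. The documents do not support this. Section 6.2.5 lists pregnancy as a reason to stop the investigational products, in the plural, and so covers both.

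**Conclusion.** The inconsistency is in the current operative text and is minor. In Arm 2, the stated post-treatment lactation window is up to 90 days shorter than both the pregnancy window and the breastfeeding restriction.

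The 90 days rest on three assumptions: AMG 404 is the last product given, the woman has left the study by day 30, and the in-study duty ends when she leaves. If that duty runs to the end of the trial and the trial is open, the figure is 0. It should not be read as a fixed gap for every woman in Arm 2.

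The rule may leave an infant exposure unreported; the text does not show that it would. Cases are expected to be close to none. No endpoint, dose decision, sample size or analysis depends on the point.

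**What to change.** In Section 9.3, replace the post-treatment lactation clause with a requirement to report lactation cases through 30 days after the last dose of AMG 596 and through 120 days after the last dose of AMG 404, whether or not the subject is still in follow-up. Naming both products matches exclusion 215. The last phrase removes the dependence on which end of study is meant.

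The cost is one sentence, which can go into the next amendment. Arm 1 is unchanged. In Arm 2, investigators carry an explicit reporting duty for up to 90 more days over a very small number of possible cases. Design, sample size and analysis are untouched.

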10. STATISTICAL CONSIDERATIONS

10.1 Study Endpoints, Analysis Sets, and Covariates

10.1.1 Study Endpoints

Primary Endpoint:

[figure not shown]
- Dose limiting toxicities (DLT), treatment-emergent adverse events, treatment-related adverse events and changes in vital signs, physical examinations, and clinical laboratory tests

Approved

Secondary Endpoint(s):

- PK parameters for monotherapy AMG 596 including, but not limited to, average steady-state concentration (C_{ss}), area under the concentration-time curve (AUC), clearance, volume of distribution and half-life ($t_{1/2}$) for serum AMG 596
- PK parameters of AMG 404 including, but not limited to, maximum observed serum concentration (C_{max}), time to achieve C_{max} (t_{max}), and AUC
- PK parameters for AMG 596 dosed in combination with AMG 404 including, but not limited to, average steady-state concentration (C_{ss}), area under the concentration-time curve (AUC), clearance, volume of distribution and half-life ($t_{1/2}$) for serum AMG 596
- Objective response (OR) as per modified RANO, time to response, response duration and time to progression (TTP); progression free survival (PFS) at 6 and 12 months after treatment initiation with AMG 596 monotherapy or AMG 596 in combination with AMG 404

Exploratory Endpoint(s):

